#### 7.3.3.2.2. Cytogenetic Response

Cytogenetic response is applicable for subjects with abnormal karyotype at baseline. Best overall response for cytogenetic response is the best response recorded before and including the time when the first progression based on altering the natural history of the disease occurs, in the order of CCyR or PCyR.

Best overall response will be summarized descriptively. Subjects with abnormal karyotype at baseline will be used as the denominators in the summary of BOR.

#### 7.3.3.2.3. Hematologic Improvement

The number of subjects who had at least one hematologic improvement in post baseline assessments along with the corresponding subcategories (ie, HI-E, HI-P, or HI-N) will be summarized descriptively.

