## 1.6. Potential Risks and Benefits of the Treatment Regimen

### 1.6.1. Potential Risks of INCB059872 Based on Preclinical Safety

The nonclinical safety program to support this IND was designed in accordance with ICH S9 for advanced cancer. In pivotal 1-month studies, INCB059872 was administered on a QOD regimen. The doses and dosing regimen for the pivotal GLP studies were selected based on the results of previous range-finding studies, where findings in the bone marrow (most prominent: abnormal megakaryocytes, decreased megakaryocytes) leading to marked thrombocytopenia resulted in subsequent internal and external hemorrhages in rats given  $\geq$  3 mg/kg (human equivalent dose 28.8 mg) QD and in dogs given  $\geq$  1 mg/kg (human equivalent dose 32.4 mg) QD. These observations suggested that QOD dosing may provide the best option for maximizing efficacy (which was similar after QD and QOD dosing regimens in nonclinical pharmacology studies) while minimizing toxicity (thrombocytopenia).

The primary INCB059872 toxicity findings included abnormal megakaryocyte morphology in bone marrow, thrombocytopenia, lower red blood parameters and higher reticulocytes, decreased mature granulocytes in the bone marrow and neutropenia, and increased monocyte count, and were attributed to the pharmacological activity of INCB059872. These findings were all partially or fully reversible after a 4-week recovery period. The toxicities produced by INCB059872 are similar to those described for a conditional LSD1 knockdown model in mice as described in literature ([Sprüssel et al 2012](#)), where LSD1 deficiency suppressed terminal granulopoiesis, erythropoiesis, and platelet production, with the exception of monopoiesis, which was promoted. [Sprüssel et al \(2012\)](#) also showed that peripheral blood granulocytopenia, monocytosis, anemia, and thrombocytopenia were reversible after restoration of LSD1 activity.

During the recovery period, a dose-dependent increase of platelet counts was observed. The maximum increase was about 3-fold compared to baseline values, and the peak time was approximately 14 days. The platelet counts returned to baseline values approximately 28 days after INCB059872 treatment cessation.

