	AML/MDS/MF	N/A	
 
Thrombocytopenia should be managed per institutional standard, relevant to the underlying disease, including initiating or increasing the frequency of platelet transfusion. If there is a suspected causal relationship to INCB059872 in the setting of a decreasing platelet count, hold INCB059872 and/or reduce INCB059872 dose for any of the following: 
 
Platelet decreased <math>> 50\%</math> compared with baseline and below <math>25 \times 10^9/L</math>.
 
Accompanied by any sign of bleeding.
 
Platelet transfusion refractory.
 
 
 
Discontinue if clinically significant bleeding suspected to be related to study treatment.
 
Discuss with medical monitor for dose modifications under any other situations not discussed above, if needed.
 

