## APPENDIX F. INTERNATIONAL WORKING GROUP RESPONSE CRITERIA FOR MYELODYSPLASTIC SYNDROME

Category	Response Criteria (Responses Must Be at Least 4 Weeks in Duration)
Complete remission (CR)	Bone marrow: $\leq 5\%$ myeloblasts with normal maturation of all cell lines Persistent dysplasia will be noted Peripheral blood: Hemoglobin (Hgb) $\geq 11$ g/dL, Platelets $\geq 100 \times 10^9/L$ , Neutrophils $\geq 1.0 \times 10^9/L$ Blasts 0%
Partial remission (PR)	All CR criteria if abnormal before treatment, except: Bone marrow blasts decreased by $\geq 50\%$ over pretreatment but still $> 5\%$ Cellularity and morphology not relevant
Marrow CR	Bone marrow: $\leq 5\%$ myeloblasts and decrease by $\geq 50\%$ over pretreatment Peripheral blood: if HI responses, they will be noted in addition to marrow CR
Stable disease (SD)	Failure to achieve at least PR, but no evidence of progression for $> 8$ weeks
Treatment failure	Death during treatment Disease progression characterized by worsening of cytopenias, increase in % of bone marrow blasts, or progression to a more advanced MDS FAB subtype than pretreatment
Disease progression (PD)	For patients with: 
 
- Less than 5% blasts: <math>\geq 50\%</math> increase in blasts to <math>> 5\%</math> blasts
 
- 5%-10% blasts: <math>\geq 50\%</math> increase in blasts to <math>> 10\%</math> blasts
 
- 10%-20% blasts: <math>\geq 50\%</math> increase in blasts to <math>> 20\%</math> blasts
 
- 20%-30% blasts: <math>\geq 50\%</math> increase in blasts to <math>> 30\%</math> blasts
 
 Any of the following: 
 
- At least 50% decrement from maximum remission/response levels in granulocytes or platelets
 
- Reduction in Hgb concentration by <math>\geq 2</math> g/dL
 
- Transfusion dependence
 

Disease transformation	Transformation to AML (30% or more blasts)
Relapse after CR or PR	At least 1 of the following: 
 
- Return to pretreatment bone marrow blast %
 
- Decrement of <math>\geq 50\%</math> from maximum remission/response levels in granulocytes or platelets
 
- Reduction in Hgb concentration by <math>\geq 1.5</math> g/dL or transfusion dependence
 

CYTOGENETIC RESPONSE	
Complete	Disappearance of the chromosomal abnormality without appearance of new ones
Partial	At least 50% reduction of the chromosomal abnormality

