### **7.3.3. Myelodysplastic Syndrome**

#### **7.3.3.1. Response Assessment**

Disease assessment for MDS subjects will be performed following the IWG Response Criteria for MDS ([Cheson et al 2006](#)). The investigator's assessment will be used to determine responses and will be logged on the eCRF. The schedule for disease assessment will be at screening, every 4 weeks during the study treatment, at the EOT visit, and every 8 to 9 weeks during the disease status follow-up.

Response status per investigator's assessment for MDS will be recorded in terms of 3 aspects: (1) altering the natural history of the disease, (2) cytogenetic response, and (3) hematologic improvement. For altering the natural history of the disease, response status will be recorded at each response assessment visit as CR, PR, marrow CR, SD, PD, treatment failure, disease transformation, or relapse after CR or PR. For cytogenetic response, response status will be recorded at each response assessment visit as CCyR, PCyR, or NA. For hematologic improvement, response status will be recorded at each response assessment visit as HI-E, HI-P, HI-N, progression or relapse after hematologic improvement, or NA. Refer to Appendix F in the Protocol for the summarized description of the IWG Response Criteria for MDS.

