### 7.3.3.2. Best Overall Response and Objective Response Rate

#### 7.3.3.2.1. Altering the Natural History of the Disease

For MDS, BOR based on altering the natural history of the disease is the best response recorded before and including the first progression, which consists of treatment failure, PD, disease transformation, and relapse after CR or PR, in the order of CR, PR, marrow CR, SD, and progression. In the case of SD, measurements must meet the SD criterion at least once on or after Day 24. When analysis requires the confirmation of CR, PR, or marrow CR, responses must be at least 4 weeks in duration and the rule in [Table 3](#) should be applied.

**Table 3: Confirmation of Complete Remission, Partial Remission, and Marrow Complete Remission for Myelodysplastic Syndrome**

First Assessment	Subsequent Assessment at 4 or More Weeks Later	Confirmed Response
CR	CR	CR
PR	PR or CR	PR
Marrow CR	Marrow CR, PR, or CR	Marrow CR

A subject is considered a responder if the subject has a best overall response of CR.

Objective response rate for MDS is defined as the proportion of responders based on altering the natural history of the disease. Subjects who do not have sufficient baseline or on-study response assessment information to be adequately assessed for response status will be included in the denominators in the calculations of ORR.

Non-confirmed BOR will be summarized descriptively, and the ORR will be estimated with its 95% CI. Best confirmed response of CR, PR, and marrow CR will be summarized descriptively. The confirmed ORR will be estimated with its 95% CI. Confidence intervals will be calculated based on the exact method for binomial distributions.

[figure not shown]

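### SAP 7.3.3.2.3 counts hematologic improvement in MDS on a single visit record, without the 4-week duration and without the baseline-cytopenia denominator that Protocol Appendix F implies (minor)

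*SAP*

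**What the plan says.** **SAP.** Section 7.3.3.1 has HI entered visit by visit: "For hematologic improvement, response status will be recorded at each response assessment visit as HI-E, HI-P, HI-N". It adds that "The investigator's assessment will be used to determine responses and will be logged on the eCRF". Section 7.3.3.2.3 then summarizes "The number of subjects who had at least one hematologic improvement in post baseline assessments", with the subtypes HI-E, HI-P and HI-N. It gives no duration, no confirmation rule and no denominator. Section 5.1 says categorical summaries give a number and a percentage, and Sections 5.3.1 and 7.1 make the full analysis set (FAS) the population for all efficacy analyses.

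**Protocol.** Appendix F is the response standard named in Protocol 7.6 and SAP 7.3.3.1. Its criteria column is headed "Responses Must Be at Least 4 Weeks in Duration", and the HI rows are in that table. Each HI row has a pretreatment condition: hemoglobin below 11 g/dL for HI-E, platelets below 100 x10^9/L for HI-P, neutrophils below 1.0 x10^9/L for HI-N. HI-P requires a rise of at least 30 x10^9/L when the baseline exceeds 20. Below 20 it requires a count above 20 and at least a doubling.

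**Platelets after stopping drug.** Protocol 1.6.1 reports for the animal recovery period: "The maximum increase was about 3-fold compared to baseline values, and the peak time was approximately 14 days". Counts were back at baseline about 28 days after stopping. Protocol 9.4.3.5 calls a rebound in subjects a possibility for which there are no human data.

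**The concern.** The protocol's criterion has two parts that the SAP's count omits: the improvement must last, and the subject must have had the relevant cytopenia to begin with. A programmer following SAP 7.3.3.2.3 literally would count one HI record at one visit and, by default, divide by all MDS subjects in the FAS.

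The duration gap matters more for this drug than for most. Its main toxicity is to platelets, holds of up to 14 days are allowed for toxicity (Protocol 5.4.7), and a rebound after stopping is considered possible. An HI-P caught in such a rebound would be a withdrawal effect reported as hematologic benefit. At stake is the credibility of a descriptive HI table.

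**Working it through.** The documents give no figure for HI to reproduce. The check has three parts.

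**1. The rules side by side**

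| | Minimum duration | Stop at first progression | Denominator |
|---|---|---|---|
| Appendix F, HI | 4 weeks (table header) | not stated | only those with the qualifying cytopenia can meet it |
| SAP 7.3.3.2.1, CR / PR / marrow CR | 4 weeks in the confirmed analysis (Table 3); unconfirmed also shown | yes | includes subjects who cannot be assessed |
| SAP 7.3.3.2.2, cytogenetic | none | yes | abnormal karyotype at baseline |
| SAP 7.3.3.2.3, HI | none | no | none stated; FAS by default |

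The SAP therefore uses both devices elsewhere in its MDS section, but neither for HI.

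**2. Could a transient rebound pass the SAP's rule but fail Appendix F?**

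Inputs: the HI-P thresholds (Appendix F) and a 3-fold peak near day 14, back to baseline near day 28 (Protocol 1.6.1, animals). Peaks below 3-fold are an assumed range. The linear rise and fall is also assumed.

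*Size.* For baseline b above 20, the fold-rise needed is (b + 30)/b: 70/40 = 1.75 at b = 40 and 90/60 = 1.5 at b = 60. A k-fold peak gives a gain of (k − 1)b, which must reach 30. Over the 95 integer baselines from 5 to 99, with exactly 20 placed in the lower band:

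| Peak | Baselines that meet HI-P | Count |
|---|---|---|
| 3-fold | 7 to 99 | 93 of 95 |
| 2-fold | 11 to 20 and 30 to 99 | 80 of 95 |
| 1.5-fold | 60 to 99 | 40 of 95 |
| 1.25-fold | none (30/0.25 = 120) | 0 of 95 |

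*Duration.* On the linear course the count is 30 above baseline from day 14 × 30/((k − 1)b) until the mirror-image day. Time above threshold is therefore 28 − 28 × 30/((k − 1)b), which for k = 3 is 28 − 420/b:

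- b = 21: 28 − 20.0 = 8.0 days
- b = 25: 28 − 16.8 = 11.2 days
- b = 50: 28 − 8.4 = 19.6 days
- b = 75: 28 − 5.6 = 22.4 days
- b = 99: 28 − 4.2 = 23.8 days

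In the lower band, doubling is reached at day 7 and lost at day 21, so the time is at most 14 days. The linear shape affects these figures but not the conclusion: any course that is back at baseline by day 28 spends less than 28 days above a raised threshold.

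*Chance of being recorded.* MDS is assessed every 4 weeks, and blood alone is allowed (Protocol Table 7). A visit during or just after a hold, or an end-of-treatment visit some days after the last dose, could fall in the window. Disease follow-up at 8 to 9 weeks would come after the rebound had gone. One record is enough under the SAP and is not enough under Appendix F.

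**3. The denominator**

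Let x subjects have HI-P, m have baseline platelets below 100, and N be all MDS subjects. The default percentage is x/N and the one matching Appendix F is x/m, so the default is m/N times the other. MDS entry sets no lower count limits and requires no cytopenia (Protocol 3.1; 3.2, criterion 4), so m is not fixed by design. If m/N were 0.6 or 0.8 (assumed), the reported percentage would be 0.6 or 0.8 of the rate among assessable subjects. This pulls down while the duration gap pushes up, and nothing makes the two cancel.

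**The case against.** **The investigator already applies Appendix F.** Status is the investigator's call, so one who reads the header would not log a short rebound, and a non-cytopenic subject cannot validly be HI-P. This stands in part: no miscount is automatic. But status is entered at each visit, when it is not yet known whether the rise will last. CR, PR and marrow CR sit under the same header, and for those the SAP did not rely on the investigator alone; it added Table 3.

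**The section promises only a number.** That is so within 7.3.3.2.3, but Section 5.1 adds a percentage to categorical summaries.

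**The rebound is an animal finding.** This stands. A reader might infer that the protocol expects a 3-fold rebound in subjects and that HI will be inflated by it. Protocol 9.4.3.5 supports only a possibility. The missing duration rule does not depend on the rebound.

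**HI decides nothing.** This stands. MDS response is CR alone (SAP 7.3.3.2.1), the TG D1 MDS futility count uses CR or marrow CR (Protocol 9.6), HI is not among the readable secondary endpoints, and the analysis is descriptive.

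**A stronger reading to avoid.** Best response ends at the first progression, "which consists of treatment failure, PD, disease transformation, and relapse after CR or PR". Appendix F lets worsening cytopenia, a hemoglobin fall of at least 2 g/dL or transfusion dependence count as failure or progression, with no exception for drug effect. A reader might infer that the SAP's cut materially lowers the MDS response rate and raises the chance of a futility stop. The documents do not support this:

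- Protocol 5.5.1 requires withdrawal at progression, with one narrow exception, and Section 6.4.2 follows only subjects who stopped for other reasons. Few later responses would exist to be lost.
- The trigger "At least 50% decrement from maximum remission/response levels in granulocytes or platelets" presupposes a response, and best response keeps that response.
- Protocol 7.6 has cytopenias used as appropriate alongside other parameters, so progression is a judgement.
- Protocol 9.6 does not invoke the best-response cut, and any figure for its effect needs a response rate and a loss fraction that neither document gives.

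**Conclusion.** The point holds, and it is minor. As written, SAP 7.3.3.2.3 can report as HI a change that fails the protocol's own criterion, and its default percentage includes subjects who could never qualify. How many subjects are affected cannot be estimated from the documents. What can be shown is that a rebound of the size and timing seen in animals would pass the HI-P threshold at all baselines from 21 to 99 x10^9/L and could not last 4 weeks. This assumes that the animal pattern carries over to humans, which is unproven, and that an assessment falls in the window. The response rate and the futility decision are unaffected.

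Separately, three protocol passages do not fit together. Appendix F counts cytopenia and transfusion dependence as progression or treatment failure. Table 5 manages thrombocytopenia in AML/MDS/MF by institutional standard, "including initiating or increasing the frequency of platelet transfusion", with hold or reduction when drug-related. Section 5.5.1 requires withdrawal at progression. The same event could be handled differently at different sites.

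**What to change.** In SAP 7.3.3.2.3:

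- Count HI-E, HI-P or HI-N as confirmed only when the same subtype is held for at least 4 weeks, with a rule parallel to Table 3. Unconfirmed HI may be shown beside it, as is done for best overall response.
- Use as denominator for each subtype the MDS subjects whose baseline (SAP 4.1.3) meets the Appendix F cytopenia: hemoglobin below 11 g/dL, platelets below 100 x10^9/L, neutrophils below 1.0 x10^9/L. For any HI, use subjects with at least one of these.
- Say how visit windows count. With ±2 days on Day 1 visits, consecutive assessments can be 28 − 4 = 24 days apart, so a strict 28 days may need a further visit.

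The cost is SAP wording and one extra summary row. The visit-level HI status, including loss of HI, and the baseline counts are already collected. Confirmed HI counts will be lower, and subjects with HI at their last assessment will appear only as unconfirmed.

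In the protocol, Appendix F, Table 5 and Section 5.5.1 should be reconciled on how cytopenia attributed to study treatment is classified. Which rule applies is for the clinical team to decide.

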#### **7.3.4. Myelofibrosis**

The MF disease assessments will be at screening, every 4 weeks during the study treatment, at the EOT visit, and every 8 to 9 weeks during the disease status follow-up. [REDACTED]

[figure not shown]

##### **7.3.4.1. Spleen Volume Reduction**

The change and percentage change from baseline as measured by MRI (or CT scan in applicable subjects) at Week 12 [REDACTED] in spleen volume will be calculated for subjects with MF in the FAS. Descriptive statistics will be calculated by dose levels for the baseline value, Week 12 value, change and percentage change from baseline to Week 12, [REDACTED]

The number of subjects with spleen volume reduction from baseline to Week 12 [REDACTED] in pre-defined categories (eg, < 0% reduction, 0% to < 10% reduction, 10% to < 35% reduction, and  $\geq$  35% reductions) will be summarized by dose levels.

## **7.4. Analysis of Other Efficacy Variables**

### **7.4.1. Eastern Cooperative Oncology Group Performance Status**

The ECOG status at scheduled assessment times will be summarized categorically by dose levels and tumor type.

## **8. PHARMACOKINETIC ANALYSES**

The PK parameters of  $C_{max}$ ,  $T_{max}$ ,  $C_{min}$ ,  $AUC_{0-t}$ ,  $t_{1/2}$ , and  $Cl/F$  (INCB059872) will be calculated from the blood plasma concentrations of INCB059872 using standard noncompartmental (model-independent) PK methods. Pharmacokinetic calculations will be performed, if appropriate, using commercial software such as WinNonlin® (Pharsight Corporation, Mountain View, CA). Nominal times will be used in all cases, except when the difference between the actual time and nominal time is greater than 15 minutes for samples collected up to 4 hours after administration and greater than 30 minutes for samples collected more than 4 hours after administration; in these cases, actual time will be used for PK analysis. Refer to Appendix C in the Protocol for a detailed list and description of the PK parameters.

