### 1.2.2. Nonclinical Drug Metabolism and Pharmacokinetics of INCB059872

The absorption, distribution, metabolism, and excretion of INCB059872, a covalent FAD-directed inhibitor for LSD1, have been characterized in rats, dogs, and monkeys. Following intravenous (IV) administration, the systemic clearance was low in monkeys and dogs (23% and 29% of hepatic blood flow, respectively) and moderate in rats (37% of hepatic blood flow). The clearance mechanisms of INCB059872 include both cytochrome P450 (CYP)-dependent metabolism and non-enzyme-dependent catabolism. The administered dose excreted in urine as intact INCB059872 varied from approximately 9.9% in rats to 7.8% in dogs and 3.5% in monkeys, indicating renal clearance as minor elimination pathways. INCB059872 exhibited a moderate steady-state volume of distribution in all 3 species (0.9-1.5 L/kg), suggesting moderate distribution. After oral administration, oral bioavailability was moderate in monkeys (37%) but high in rats (70%) and dogs (100%). The terminal elimination half-life was 1.0 hour in rats, 1.2 hours in dogs, and 3.3 hours in monkeys. Despite a short half-life, sustained pharmacological activity was observed *in vitro* and *in vivo*, presumably a result of irreversible or covalent inhibition of LSD1, ie, a pharmacokinetic (PK)-PD divergence is expected for this mode of inhibition by INCB059872. Based on allometric scaling, the terminal elimination half-life in human is projected to be approximately 3 hours, and the oral bioavailability is projected to be 70%. Significant antitumor effects were observed in mice when peak plasma concentration exceeded the EC50 in the whole blood assay with either QD or QOD dosing. Based on preclinical PK-PD relationship assessment, the projected clinical dose for efficacy in patients is 2 mg QOD, which is expected to provide plasma concentrations exceeding the EC50 of 0.023  $\mu$ M (based on THP-1 spiked whole blood assay with CD86 induction) for 2 hours, the total steady-state plasma AUC0-48 and Cmax is estimated to be approximately 0.2  $\mu$ M·h and 0.05  $\mu$ M, respectively.

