## 7.8. Pharmacokinetic Assessments

### 7.8.1. Blood Sample Collection

Pharmacokinetic samples will be obtained at the visits indicated in the Schedule of Laboratory Assessments (Table 8) to evaluate plasma PK parameters as described in Appendix C. For PK sample collection, the following will be recorded:

- The exact date and time of the blood sample.
- The date and time of the last dose of study drug before blood collection (if applicable).
- The time of the most recent meal.

Subjects will receive reminder cards in advance of the study visit providing instructions to prepare for the visit (see Section 7.10.1). Instructions for plasma preparation and sample shipping will be provided in the Laboratory Manual.

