### 7.8.4. Food-Effect Pharmacokinetic Testing

Pharmacokinetic testing for food effect on drug exposure will be performed on approximately 8 subjects enrolled in TG B1, Part 2; this will occur on Cycle 2 Day 1.

Subjects will have been fasted from food (not including water) for at least 4 hours. A standardized high-fat, high-calorie breakfast will be given to these subjects approximately 30 minutes before administration of study drug. Subjects must consume the entire breakfast within 25 minutes, and INCB059872 administration will begin 5 minutes after completing breakfast.

A high-fat, high-calorie meal (approximately 800-1000 calories, approximately 50% calories from fat) ([FDA 2002](#)) may consist of the following:

- 2 eggs fried in butter
- 2 strips of bacon
- 1 English muffin with butter
- 4 oz hash brown potatoes
- 8 oz whole milk

Alternative menus with the same caloric and fat content may be substituted with the prior approval of the study sponsor.

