## APPENDIX C. PHARMACOKINETIC ANALYTICAL PARAMETERS

$C_{ave}$	Average steady-state plasma concentration ( $AUC_{0-12h}/12h$ or $AUC_{0-24h}/24h$ )
$C_{max}$	Maximum observed plasma concentration
$C_{min}$	Minimum observed plasma concentration during the dosing interval
$T_{max}$	Time to maximum plasma concentration
$AUC_{0-t}$	Area under the single-dose plasma concentration-time curve from Hour 0 to the last quantifiable measurable plasma concentration, calculated by the linear trapezoidal rule for increasing concentrations and the log trapezoidal rule for decreasing concentrations
$AUC_{0-\tau}$ (ie, $AUC_{0-12h}$ or $AUC_{0-24h}$ )	Area under the steady-state plasma concentration-time curve over 1 dosing interval calculated by the linear trapezoidal rule for increasing concentrations and the log trapezoidal rule for decreasing concentrations
$\lambda_z$	Apparent terminal phase disposition rate constant, where $\lambda_z$ is the magnitude of the slope of the linear regression of the log concentration versus time profile during the terminal phase
$t_{1/2}$	Apparent plasma terminal phase disposition half-life (whenever possible), where $t_{1/2} = (\ln 2) / \lambda_z$
$Cl/F$	Oral dose clearance
$V_z/F$	Apparent oral dose volume of distribution
Fluctuation	Steady-state fluctuation ( $[C_{max} - C_{min}] / C_{ave}$ )

In addition, the following PK parameters may be calculated, whenever possible, for each subject based on the urine INCB059872 concentrations:

$A_e$	Amount of drug excreted in the urine over sampling interval
$Cl_r$	Renal clearance, where $Cl_r = A_e/AUC$
% Excreted or $f_e$	percent excreted in the urine, where % Excreted = 100 ( $A_e/dose$ )

Pharmacokinetic calculations will be performed, if appropriate, using commercial software such as WinNonlin®. Additional details of analyses will be described in the statistical analysis plan.

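### Noncompartmental PK analysis places every in-window postdose sample at its nominal time although exact times are recorded, adding avoidable random error to individual half-life and Cl/F

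*SAP*

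**What the plan says.** SAP section 8 sets the rule for noncompartmental analysis: "Nominal times will be used in all cases, except when the difference between the actual time and nominal time is greater than 15 minutes". The 15-minute limit applies through the 4 h sample; the later limit is "greater than 30 minutes for samples collected more than 4 hours after administration". Only beyond these limits does actual time replace nominal time. Protocol 9.4.4 carries identical wording.

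Protocol Table 10 sets the postdose collection windows: ±10 min at 0.5 h, ±15 min at 1, 2 and 4 h, and ±30 min at 6 h, which is the last sample.

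Protocol 7.8.1 requires sites to record "The exact date and time of the blood sample", and also when the preceding dose was taken. Actual elapsed time since dose is therefore available.

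The parameters derived under this rule (Cmax, Tmax, Cmin, AUC0-t, half-life and Cl/F) are secondary endpoints. Protocol Appendix C runs AUC0-t to the last quantifiable concentration, "calculated by the linear trapezoidal rule for increasing concentrations and the log trapezoidal rule for decreasing concentrations". Neither document explains the preference for nominal times or plans a sensitivity analysis with actual times.

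**The concern.** A rule of this kind is normally meant to ignore trivial deviations and to use the true time when the deviation matters. Here the switch point is at or outside the edge of each window, so for postdose samples taken as planned it never operates. A 0.5 h sample may be 10 minutes off, a third of its nominal time, and still be placed at 0.5 h. One that is 10 to 15 minutes off is out of window and is still placed at 0.5 h.

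The sampling design makes timing relevant. The Protocol projects that "the terminal elimination half-life in human is projected to be approximately 3 hours", and sampling stops at 6 h. Few points can define the terminal slope, and the last of them has the widest window. Error in that slope passes into half-life and, through the extrapolated area, into Cl/F. What is at stake is the precision of individual values for two secondary PK parameters.

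**Working it through.** The documents give no precision figure for PK, so there is none to reproduce.

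**1. Switch limits against windows (SAP 8; Protocol Table 10)**

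| Nominal time | Window | Actual time used only if deviation exceeds |
|---|---|---|
| 0.5 h | ±10 min | 15 min |
| 1, 2, 4 h | ±15 min | 15 min |
| 6 h | ±30 min | 30 min |

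Because the deviation must exceed the limit, no in-window postdose sample can trigger the switch.

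**2. Half-life, timing error alone.** Assume a log-linear terminal phase fitted at nominal 2, 4 and 6 h, with true times shifted by d2, d4 and d6 hours. The least-squares slope on these equally spaced times is (y6 − y2)/4, so

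fitted slope / true slope = 1 + (d6 − d2)/4.

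- Worst in-window cases for a true 3 h half-life:
  - d6 = +0.5, d2 = −0.25: ratio 1.1875, half-life 3/1.1875 = 2.53 h.
  - d6 = −0.5, d2 = +0.25: ratio 0.8125, half-life 3/0.8125 = 3.69 h.
- Uniform deviations: the variance is (range)²/12, so 1²/12 = 0.0833 for d6 and 0.5²/12 = 0.0208 for d2. SD of the ratio = √0.1041/4 = 8.1%.
- Triangular deviations: the variance is half of that, giving about 5.7% on the slope and 5.8% on half-life.
- Bias: half-life is the reciprocal of the slope, so the mean shift is about 0.081² = 0.0066, or +0.6%.

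These relative figures do not depend on the assumed half-life.

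**3. Half-life with residual error.** Assume a 10% residual (assay plus model) error. The log-slope SD is 0.10/√8 = 0.0354 per h. Against ln2/3 = 0.231 per h this is 15.3%. Adding timing error gives √(15.3² + 8.1²) = 17.3%. Simulation of half-life itself, which is slightly skewed, gives about 16% with actual and 18% with nominal times.

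**4. Simulation for Cl/F and AUC.** 200,000 profiles were drawn from a one-compartment oral model at the Table 10 times, with uniform in-window deviations, linear-up/log-down AUC and the terminal slope from 2, 4 and 6 h. The absorption rate was varied from 1.5 to 6 per h and the half-life from 1.5 to 6 h. The model form and these ranges are assumptions.

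- Cl/F (dose over AUC to infinity), timing-error SD: 3.4% to 6.6% with nominal times, 0.3% to 2.0% with actual times. At a 3 h half-life and absorption rate 3 per h it is 4.6% against 0.4%; with 10% residual error, 9.0% against 7.6%.
- AUC0-t, CV without residual error, absorption rate 3 per h:

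| Half-life | Nominal | Actual, unadjusted |
|---|---|---|
| 1.5 h | 2.9% | 1.4% |
| 3 h | 1.7% | 2.6% |
| 6 h | 1.1% | 3.7% |

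At 3 h with 10% residual error the CVs are 5.2% and 5.5%. Unadjusted actual-time AUC0-t ends anywhere from 5.5 to 6.5 h, and this offsets the gain. Carried to a common 6 h using the terminal slope, the actual-time SD at 3 h without residual error is 0.5%.

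**5. Group means.** With an assumed 40% between-subject CV and n = 8, the SE of a mean half-life is 40%/√8 = 14.1%. Adding a 9% timing SD gives √(0.40² + 0.09²)/√8 = 0.41/2.83 = 14.5%.

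**The case against.** The strongest case against the point is that the rule is a prespecified convention, identical in both documents, which does switch to actual time for larger deviations. PK is exploratory, Protocol 9.3 plans no formal tests, and the expansion doses were chosen on safety and tolerability. No decision in the documents is shown to turn on a few percent in half-life. The 8% assumes deviations spread over the whole window and a particular three-point fit, neither of which the documents specify. The 2.5 to 3.7 h range needs the 2 h and 6 h draws at opposite window limits in the same subject. Once residual error is allowed for, three terminal points over 6 h account for most of the imprecision.

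All of this stands, and it sets the severity. It does not give a reason to prefer nominal times when exact ones are recorded.

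A reader might also infer that nominal times damage AUC0-t and therefore the food-effect comparison, planned in "approximately 8 subjects enrolled in TG B1, Part 2". The documents do not support that. Appendix C ends AUC0-t at the last quantifiable sample, so a bare switch to actual times makes the end point vary between subjects and is slightly worse at the projected half-life. For a within-subject fed-to-fasted comparison at 3 h, the log-scale SD from timing is 2.5% with nominal and 3.7% with unadjusted actual times (7.3% and 7.8% with 10% residual error). The readable text of SAP 8 and Protocol 9.4.4 defines no food-effect ratio. Nor does the 0.5 h example bear on half-life, because that sample is not in the terminal fit.

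**Conclusion.** The point holds as a low-severity improvement. Under SAP 8 and Protocol 9.4.4 no in-window postdose sample is analysed at its recorded time. The cost is random error in individual half-life (SD about 8% with uniform deviations, 5.8% with triangular) and in Cl/F (about 3% to 7%), nearly all of it removable with data already collected. With 10% residual error at a 3 h half-life the practical gain shrinks to about 18% against 16% for half-life.

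The error is almost unbiased, so it would be wrong to read this as a distortion of the PK conclusions. The effect on group means is small and Cmax is unaffected. No benefit is claimed for AUC0-t unless a common end time is also set.

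The existence of the gap rests only on the documents. Its size rests on the assumed deviation distribution, the 2, 4 and 6 h fit, the one-compartment model and the assumed residual error.

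**What to change.** In SAP 8 and Protocol 9.4.4:

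- Derive all noncompartmental parameters (terminal slope, half-life, AUC, Cl/F) from actual elapsed time since dose.
- Compare AUC, including fed against fasted, over a common interval such as 0 to 6 h. Where the last sample is not at exactly 6 h, interpolate or extrapolate to 6 h with the terminal slope. The AUC part of the change should not be made without this rule.
- Keep nominal times for by-timepoint concentration summaries and mean plots.

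The cost is one added AUC end-time rule and a wording change in both documents. No new samples, visits or data fields are needed. If the SAP is changed before the Protocol, SAP 11.1 should record the departure.
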